3. HYPOTHESIS OR STUDY QUESTION

Main Hypothesis:

The application of a cognitive stimulation program with virtual reality will be well accepted by patients with mild cognitive impairment.

Secondary Hypotheses:

- Virtual reality interventions will be perceived as useful and motivating by patients, promoting positive adherence to the cognitive stimulation program.
- Patients will improve their cognitive performance (attention and memory) on cognitive scales after the sessions.
- Virtual reality interventions will be perceived as useful and applicable as a tool in the clinical practice of cognitive stimulation by healthcare professionals.

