5.4 Study variables

5.4.1 Variables result, exposure or effect

Main Outcome Variable:

Acceptability and usability of VR exercises: This will be measured using a user satisfaction questionnaire and the System Usability Scale (SUS). HE will managen after the last session (the eighth).

Secondary Outcome Variables:

Cognitive function (memory and attention), measured through standardized tests: - Specific to attention and memory (Digits, TMT [Annex 3], SDMT [Annex 4]).

- General cognitive function tests:
- Montreal Cognitive Assessment (MoCA) [anexo 5]
- Mini-Mental State Examination (MMSE) [anexo 6]

The evaluations will be carried out before starting the training program and at the end of it (after the eighth session).

Usability of the system by professionals:

This will be evaluated using the System Usability Scale (SUS) for patients and professionals [Annex 7 and 8]. It will be administered to professionals after completing the training program.

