5.7 Statistical analysis

The data collected during the study will be analyzed using statistical methods appropriate for each type of variable. All analyses will be performed using statistical software SPSS 27.0.

Acceptability and Usability: Scores obtained on the System Usability Scale (SUS) will be analyzed descriptively to provide an overall measure of the acceptability and usability of the VR intervention.

Cognitive function: Depending on the normality of the variables, statistical tests will be applied to compare scores (parametric Student's T or non-parametric Wilcoxon (in the case of failure to comply with the assumption of normality).

Demographic and clinical variables: Correlation and multiple regression analyzes will be used to examine relationships between demographic and clinical variables (e.g., age, gender, etiology, education) and changes in acceptability, usability, cognitive function, and quality of life.

The hypotheses will be evaluated at the significance level of p < 0.05 (95% confidence level). As this is a pilot study, the results will be used primarily to generate hypotheses for future research and to provide effect size estimates that may be useful for sample size calculation in future studies.

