6- Physical safety: There is a risk of patients tripping or falling while using VR due to spatial disorientation. To mitigate this risk, patients will be seated during VR sessions and will be

closely supervised by healthcare personnel to ensure their safety. Additionally, the area around the patient will be free of obstacles.

7- Withdrawal effect: If the VR tool is withdrawn after the conclusion of the study, the patients who participated may show less interest in continuing with the conventional cognitive stimulation program. To mitigate this risk, if the results of the study are positive and show significant benefits for patients, a commitment will be made to keep this tool in use within the cognitive stimulation program.

Benefits

1- Cognitive stimulation: VR offers an interactive and attractive medium for cognitive stimulation, which can be more motivating and attractive for patients than traditional therapies.

2- Improved emotional well-being: Patients may experience an improvement in their emotional well-being when participating in immersive VR experiences, especially if the sessions are designed to be enjoyable and fun.

3- Contribution to research: Patients will participate in a study that may contribute to improving the understanding and treatment of cognitive impairment.

To ensure the safety and comfort of participants, healthcare personnel will receive extensive training in the use of VR. All necessary precautions will be taken to minimize risks and participants will be closely monitored for any side effects. It is hoped that participation in the study can have a positive impact on the cognition and emotional well-being of the participants, and that it contributes to research in this field.

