ANNEX 3. Attention and memory test: TMT

Trail Making Test (TMT) Parts A & B

Instructions:

Both parts of the Trail Making Test consist of 25 circles distributed over a sheet of paper. In Part A, the circles are numbered 1 - 25, and the patient should draw lines to connect the numbers in ascending order. In Part B, the circles include both numbers (1 - 13) and letters (A - L); as in Part A, the patient draws lines to connect the circles in an ascending pattern, but with the added task of alternating between the numbers and letters (i.e., 1-A-2-B-3-C, etc.). The patient should be instructed to connect the circles as quickly as possible, without lifting the pen or pencil from the paper. Time the patient as he or she connects the "trail." If the patient makes an error, point it out immediately and allow the patient to correct it. Errors affect the patient's score only in that the correction of errors is included in the completion time for the task. It is unnecessary to continue the test if the patient has not completed both parts after five minutes have elapsed.

Step 1: Give the patient a copy of the Trail Making Test Part A worksheet and a pen or pencil.

Step 2: Demonstrate the test to the patient using the sample sheet (Trail Making Part A – SAMPLE).

Step 3: Time the patient as he or she follows the "trail" made by the numbers on the test. Step 4: Record the time.

Step 5: Repeat the procedure for Trail Making Test Part B.

Scoring:

Results for both TMT A and B are reported as the number of seconds required to complete the task; therefore, higher scores reveal greater impairment.

Average Deficient Rule of Thumb Trail A 29 seconds > 78 seconds Most in 90 seconds Trail B

75 seconds > 273 seconds Most in 3 minutes

Sources:

- Reitan RM. Validity of the Trail Making test as an indicator of organic brain damage. *Percept Mot Skills*. 1958;8:271-276.

Trail Making Test Part A

Patient's Name: Date:

Trail Making Test Part A – SAMPLE

Trail Making Test Part B

Patient's Name: Date:

Trail Making Test Part B – SAMPLE

Institut Català de la Salut

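### Section 5.7 judges one hypothesis of cognitive improvement at p < 0.05 on about six scores, with no deciding score and no success rule, so the stated level does not hold for that hypothesis

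*Combined protocol and SAP*

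**What the plan says.** Section 3 (secondary hypotheses) puts cognition in one directional statement: "Patients will improve their cognitive performance (attention and memory) on cognitive scales after the sessions".

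Section 5.4.1 lists the secondary outcomes that serve it. The first group is "Specific to attention and memory (Digits, TMT [Annex 3], SDMT [Annex 4"]). The second group, general cognitive function, holds "Montreal Cognitive Assessment (MoCA") and "Mini-Mental State Examination (MMSE"). All are measured before the programme and after the eighth session. Annex 3 treats the Trail Making Test as two scores: "Results for both TMT A and B are reported as the number of seconds required to complete the task".

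Section 5.7 says that for cognitive function "statistical tests will be applied to compare scores", by Student's t or Wilcoxon according to normality, and then: "The hypotheses will be evaluated at the significance level of p < 0.05 (95% confidence level"). The sentence after that describes the pilot's results as mainly a source of hypotheses and of effect sizes for planning later studies. No section names a key cognitive score, a success rule or a multiplicity adjustment.

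Section 7.1, on the risk of patients losing interest once the tool is withdrawn, promises to keep the tool in use "if the results of the study are positive and show significant benefits for patients". It does not define the term.

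**The concern.** A significance level belongs to a decision. Here the decision is whether cognition improved, but the 0.05 attaches to each score separately. With several scores and no rule for combining them, the hypothesis itself is not tested at 0.05. An investigator who finds one significant score out of six could report improvement, and nothing in the plan prevents it.

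Three uses of the results are exposed:

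- **Effectiveness.** Section 4.2 says the before/after change is measured in order to judge whether the programme is effective, although 5.6 and 5.8 say that demonstrating effectiveness is not the purpose.
- **Planning the next study.** With 20 patients, a paired t test is significant only if the observed standardized change reaches about 0.47. If the score that happened to be significant is carried forward, the next trial would be planned on an inflated effect.
- **Retention of the tool.** The commitment in 7.1 uses a word that a reader could take to mean statistical significance.

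**Working it through.** The 0.05 is a chosen level, not a derived figure, and it agrees with the stated 95% confidence (1 − 0.95 = 0.05). The sample size of 20 is justified in 5.6 by the pilot's nature and by capacity, so there is no power calculation to reproduce.

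**Inputs**

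- Number of scores, k. Digits 1 + TMT 2 + SDMT 1 + MoCA 1 + MMSE 1 = 6 (5.4.1, Annex 3). Only the attention and memory tests: 1 + 2 + 1 = 4. If Digits forward and backward are scored separately, which is not stated, k = 7. Section 6.1 also mentions assessments during the programme and quality of life, which could raise the count further.
- Level per test: 0.05 (5.7). The sidedness is not stated. I take it as two-sided, so 0.05/2 = 0.025 lies in the improvement direction.
- n = 20, one comparison per score, paired form assumed from the before/after design.
- Correlation between change scores: not given. Range 0 to 0.9 assumed.
- No true change in any score, and any single significant score read as improvement.

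**Independent scores**

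False improvement on at least one score = 1 − (1 − 0.025)^k; significant in either direction = 1 − (1 − 0.05)^k.

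- k = 4: 1 − 0.975^4 = 9.6%; 1 − 0.95^4 = 18.5%
- k = 6: 1 − 0.975^6 = 14.1%; 1 − 0.95^6 = 26.5%
- k = 7: 1 − 0.975^7 = 16.2%; 1 − 0.95^7 = 30.2%

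**Correlated scores**

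I used 40,000 simulated trials with k = 6, n = 20, paired t tests and equal correlation between normal change scores. At correlation 0 the simulation gave 14.2% and 26.4%, in line with the formulas.

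| Correlation | False improvement | Either direction |
|---|---|---|
| 0 (formula) | 14.1% | 26.5% |
| 0.5 | 10.8% | 21.1% |
| 0.7 | 8.3% | 16.7% |
| 0.9 | 5.5% | 11.1% |

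One two-sided test gives 2.5% in the improvement direction and 5% in either direction. False improvement is therefore 14.1/2.5 = 5.6 times its single-test value at correlation 0, 4.3 times at 0.5, 3.3 times at 0.7 and 2.2 times at 0.9.

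**Threshold for a significant change**

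The two-sided 5% critical value of t with 19 degrees of freedom is 2.093, and 2.093/√20 = 0.47.

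**Price of correcting all six instead**

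The first Holm or Bonferroni threshold is 0.05/6 = 0.0083. Power for a standardized paired change of 0.66 falls from about 80% to about 52%, and the change detectable with 80% power rises from 0.66 to 0.86.

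**The case against.** The strongest reply is that this is a declared pilot. Cognition is secondary, the main outcome is analysed descriptively, and the sentence after the one on significance makes the results chiefly hypothesis-generating. Many statisticians would not require correction of secondary outcomes in such a study. That stands, and it is why the point is minor. It does not remove the formal evaluation at 0.05, which chiefly applies to these cognitive comparisons.

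Next, no section says that one significant score is enough. The hypothesis speaks of scales in the plural, and on a narrower reading only four scores bear on attention and memory. This also stands: six is a reading, and the any-one rule is an assumption that the plan's silence permits.

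Three stronger readings are tempting, and the documents do not support them:

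- A reader might infer that a false improvement is several times likelier than the stated 5%. With two-sided tests it is 14.1/5 = 2.8 times at correlation 0, 2.2 times at 0.5 and 1.1 times at 0.9. Larger multiples need the 2.5% comparator or must count significant worsening as well.
- A reader might infer that 7.1 makes the commitment hang on p < 0.05 for a cognitive score. It mentions neither p-values nor cognition nor 5.7, and the benefits listed in the same section include motivation and emotional well-being. The term is undefined, and the link is only an inference.
- A reader might infer that a formal correction is obligatory. In a pilot of 20 patients, the loss of power makes that a trade-off.

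**Conclusion.** The gap is real and minor. The plan evaluates one cognitive hypothesis at 0.05 on about six scores without saying which score, or how many, would decide it. If any one significant score is read as improvement, the chance of a false one when nothing changes runs from about 14% (independent scores) to 5.5% (correlation 0.9), against 2.5% for a single test. With four independent scores it is 9.6%. These figures rest on two-sided paired t tests, 20 complete patients, equal correlations and the any-one rule. None of the last three is given by the plan as a basis for the analysis, apart from the target of 20 patients.

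The rates cover chance error only. With no control group, practice effects and regression to the mean can also produce a significant change, and no multiplicity rule protects against them.

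**What to change.** - **Section 5.7, before data collection:** name one attention or memory score, of the investigators' choosing, as the only one on which the cognitive hypothesis is evaluated at 0.05. For TMT, specify the part.
- **Section 5.7, other scores:** report them as exploratory mean changes with 95% confidence intervals, and state that an interval excluding zero is not a claim of improvement. That statement is needed because a t-based 95% interval excluding zero is the same event as p < 0.05.
- **Section 5.7 or 5.8:** state that, without a control group, even a significant result on the named score cannot be separated from practice effects or regression to the mean.
- **Section 7.1:** say which result the commitment refers to, so that an isolated significant score does not trigger it.

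The cost is a few sentences, with no extra patients, visits or tests. The named score keeps its full 0.05 and loses no power, and estimates with intervals serve the plan's own aim of supplying effect sizes. The downside is that the other scores can no longer support a claim of improvement. Holm across all scores is an alternative if every one must be tested, at the loss of power shown above.

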5.8 Limitations

1. Study design and sample size

Limitation: The study is characterized by being a non-randomized pilot, without a control group, and of short duration. Likewise, it is carried out with a sample of 20 participants, which may limit its representativeness.

Mitigation strategy: The preliminary nature of the study and the resources available at the El Carme Socio-Health Center in Badalona influence the decision to have a small sample size. The main objective is to evaluate the usability and acceptability of the VR intervention, rather than to demonstrate its effectiveness. Although the sample size is small, it is expected to reflect the diversity of the patient population, providing a deep understanding of how different types of patients may interact with VR. Furthermore, the results of the pilot study will provide crucial preliminary information for future larger and well-controlled investigations.

2. Outcome measures

Limitation: Measures of acceptability, usability, and cognitive function are largely self-reported, which may introduce bias.

Mitigation strategy: Despite this limitation, the best available tests have been selected, recognizing that no test is perfect and that all have some limitations. In future research, we will seek to incorporate additional objective measures, if possible.

3. Variability in VR exposure and effect of healthcare personnel

Limitation: Individual experience with VR may vary due to factors such as degree of cognitive impairment, familiarity with the technology, and ability to follow instructions. Furthermore, the improvement in cognitive function could be influenced by the interaction with healthcare personnel during VR sessions.

Mitigation strategy: An attempt will be made to standardize the administration of VR as much as possible and variables such as the duration and content of the interaction with healthcare personnel will be controlled.

4. Training of health personnel

Limitation: Healthcare personnel must be familiar with this technology for its effective implementation.

Mitigation strategy: Extensive training and ongoing support will be offered to healthcare personnel. Additionally, it will be built on an existing VR application, designed specifically for the hospital environment.

These limitations have been taken into account during the planning of the study and will be discussed in detail in the presentations and publications resulting from the study. Findings from the pilot study will be used to inform and improve the design of future research in this field.

6. SOURCES OF OBTAINING AND MANAGING DATA

6.1 Data source

Data collection in this pilot study will be carried out through primary sources. Data will be obtained directly from participants:

The acceptability and usability of the VR exercises will be measured through questionnaires that participants will complete after each VR session.

Cognitive function and quality of life will be measured through standardized tests that participants will complete before, during and after the VR training program.

Variables such as age, gender and degree of cognitive impairment will be collected through interviews and medical records.

Exposure to other treatments will be recorded through interviews with participants and review of their medical records.

6.2 Data management and quality control

Data recording will be carried out using standardized spreadsheet templates to ensure

consistency in data collection. The data of each participant will be registered using a unique identification code for each participant to maintain confidentiality.

To ensure data security, data will be stored in a secure folder within the BSA intranet. This folder will have restricted access to the main investigators of the study to maintain the privacy of the data and avoid unauthorized manipulations.

Finally, before analyzing the data, it will be cleaned and reviewed to detect and correct any inconsistencies or errors. This stage will ensure that the results of the statistical analysis are based on accurate and valid data.

7. PROTECTION OF PERSONS UNDER INVESTIGATION

7.1 Benefit-risk evaluation for research subjects

This interventional study uses virtual reality (VR) for cognitive stimulation of patients with cognitive impairment. The following potential risks and benefits to participants have been identified, along with specific mitigation strategies for the identified risks.

Risks and Mitigation Strategies:

1- Side effects of VR: Some patients may experience dizziness or disorientation with VR. To mitigate this risk, static or smooth motion VR experiences will be designed, and the technology will be introduced gradually. Side effects will be carefully monitored, especially in patients with conditions that may increase risk.

2- Patient acceptance: Since VR is a relatively new technology, it can be intimidating for some patients. To overcome this barrier, the potential benefits of VR will be effectively communicated and patient concerns will be proactively managed. Engagement with healthcare personnel during the process can improve patient acceptance and adherence.

3- Technical problems: Like any technology, VR can face technical problems such as hardware or software failures, or Internet connectivity problems. To mitigate this risk, backup equipment will be available and appropriate training will be provided to healthcare personnel to handle VR equipment. Fast and efficient technical support will also be guaranteed to resolve any issues that may arise.

4- Technical problems: Like any technology, VR can face technical problems such as hardware or software failures, or Internet connectivity problems. To mitigate this risk, backup equipment will be available and appropriate training will be provided to healthcare personnel to handle VR equipment. Fast and efficient technical support will also be guaranteed to resolve any issues that may arise.

5- Exclusion of certain patients: Some patients may not be able to participate due to severe cognitive impairment, dizziness, certain visual impairments or other health conditions, which could potentially lead to feelings of exclusion or frustration. To mitigate this risk, communication with patients about the limitations of who can participate in the study will be clear, explaining health and safety reasons. For those patients who are unable to participate, other alternative activities or interventions will be explored.

6- Physical safety: There is a risk of patients tripping or falling while using VR due to spatial disorientation. To mitigate this risk, patients will be seated during VR sessions and will be

closely supervised by healthcare personnel to ensure their safety. Additionally, the area around the patient will be free of obstacles.

7- Withdrawal effect: If the VR tool is withdrawn after the conclusion of the study, the patients who participated may show less interest in continuing with the conventional cognitive stimulation program. To mitigate this risk, if the results of the study are positive and show significant benefits for patients, a commitment will be made to keep this tool in use within the cognitive stimulation program.

Benefits

1- Cognitive stimulation: VR offers an interactive and attractive medium for cognitive stimulation, which can be more motivating and attractive for patients than traditional therapies.

2- Improved emotional well-being: Patients may experience an improvement in their emotional well-being when participating in immersive VR experiences, especially if the sessions are designed to be enjoyable and fun.

3- Contribution to research: Patients will participate in a study that may contribute to improving the understanding and treatment of cognitive impairment.

To ensure the safety and comfort of participants, healthcare personnel will receive extensive training in the use of VR. All necessary precautions will be taken to minimize risks and participants will be closely monitored for any side effects. It is hoped that participation in the study can have a positive impact on the cognition and emotional well-being of the participants, and that it contributes to research in this field.

7.2 Information to subjects and informed consent

The research team is committed to ensuring that all potential participants receive clear, complete and understandable information about the study. This information will include details about the purpose of the research, the procedures that will be carried out, the possible benefits and risks, and the management of the confidentiality of personal information and the results of the study.

To achieve this goal, the following methods will be used:

Informed Consent Document: An Informed Consent document has been developed and will be provided to each potential participant. This document will include detailed information about the study, including the purpose, procedures, possible risks and benefits. The document will also emphasize that participation in the study is completely voluntary, and that the individual has the right to withdraw from the study at any time without repercussions on his or her medical care.

Information Sheet for Participants: Potential participants will be provided with an Information Sheet, which will complement the Informed Consent document, offering a summary of key study information in an easy-to-understand format.

Information Sessions: During meetings with potential participants, they will be given the opportunity to ask questions and discuss any concerns they may have. Before obtaining consent, it will be verified that the participant has fully understood the information provided. To facilitate understanding, all aspects of the study will be explained using simple

and accessible language.

Consent of Legal Representatives: In cases of patients with moderate cognitive impairment who may have difficulties understanding the information provided or giving their consent, informed consent will be requested from their legal representative. The legal representative will be present during the explanation of the information and obtaining consent.

The principle of autonomy of the participants will be respected at all times. No individual will be included in the study without having provided valid informed consent, either directly or through their legal representative. A record of the consent process will be maintained for each participant to ensure transparency and accountability.

